The complications particularly related to the procedure include bleeding, infection, or damage to surrounding structures during the creation of the cranial access or placement of the sheath. During evacuation of the hemorrhage with the Artemis Device, there is the possibility of inducing or encountering an additional hemorrhage in the operative bed. In a retrospective multicenter study of the Apollo procedure for the treatment of ICH, re-bleeding was encountered in 2 of 29 subjects (6.9%).⁵⁶ There may be residual fluid or blood requiring additional surgery in the future.

The risk related to the general anesthetic in this patient population is estimated to be approximately 1 – 5% for major morbidity and mortality (e.g. airway management issues, aspiration, hypotension or drug reaction), given that their American Stroke Association score would typically be 4 or 4e in this category of patients.^{57,58} A thorough risk analysis was performed as part of design control recommendations of the Quality System Regulation (21 CFR 820).

Best medical management (MM) will be provided as specified in the AHA/ESO guidelines.^{18,59} As such, for subjects randomized to the MM arm of the study, there is no additional risk. With the natural history of ICH/IVH and standard of care, there are expected medical events, or expected adverse experiences, that are listed below. Since these medical events are expected in the disease process or after MM, the events are thus expected to occur in any patients with the disease irrespective of the treatment arm. Best medical management (MM) will be provided as specified in the AHA/ESO guidelines.^{19,60} As such, for subjects randomized to the MM only arm of the study, there is no additional risk.

EXPECTED EVENTS	
Nervous System	Other Systems
Cerebral Edema and Mass Effect	Acute Kidney Injury
Brain Stem Compression	Acute Respiratory Distress Syndrome
Brain Herniation	Aspiration
Brain Re-bleeding near Initial Hemorrhage Site	Catheter-related vascular infections
Catheter Tract Bleeding/Hemorrhage Enlargement	Deep Vein Thrombosis
Cerebral Infarction	Dysphagia
Cerebritis	Fever/Hyperthermia

Coma	Hyponatremia
Death	Hypoxia
Decreased Level of Consciousness	Hypercapnia
Delirium	Hyperglycemia/Hypoglycemia
Diaschisis	Hypertension (Induced or Not Induced)
Elevated ICP	Hypotension (Induced or Not Induced)
Headache	Impaired Nutritional Status
Hydrocephalus	Infectious Complications
Intracranial Abscess	Nausea

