7.6.1 Adverse Events

Adverse events or adverse device effects must be recorded by the investigator on the CRFs and must be carefully monitored during the study. All adverse events will be collected starting at enrollment through discharge and/or 7 day visit. After discharge and/or 7 day visit, all SAEs and neurological AEs are reportable through final follow-up visit.

Minimum requirements of data to be recorded are: type of event, duration of event (start through end), seriousness, action taken, outcome, and causality.

In order to ensure prompt reporting of AEs, we require that all reportable AEs (as well as all related study data) be entered timely into the Electronic Data Capturing (EDC) web-based database. All UADE should be reported immediately by calling Penumbra Clinical Affairs and all SAEs should be reported in the EDC within 72 hours of the study site staff first being made aware of the occurrence of the SAE. If the EDC system is unavailable, a written report can be sent via email to Penumbra.

The investigator must report the SAE or ADE to the IRB/EC according to local requirements. Reporting time frames should comply with local or national requirements. In addition, the investigator should report to the Sponsor and IRB/EC any device malfunctions that could have led to a SAE, if required by national regulations or by local authorities.

For the purpose of reporting within this protocol, pre-existing conditions or planned procedures for pre-existing conditions are not reported as AEs unless there is worsening of the condition with an increase in severity or frequency during the course of the investigation. An event does not need to be reported as a SAE if it represents a relapse or an expected change or progression of the condition. This type of event is considered an AE. All deaths should be reported regardless of causality. When reporting a death, the primary condition or

diagnosis that contributed to the fatal outcome should be reported as a SAE with an outcome of death. If the cause of death is unknown, please report “unknown cause of death” as an SAE.

Detailed form and narrative reports of the following specific adverse events will be obtained:

- Death (all cause) within 30 days of enrollment
- Death within 7 days of enrollment: Immediate periprocedural death

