7.6.1.2 Definitions

- **Adverse Event (AE):** An AE is any undesirable clinical event occurring to a patient, during a clinical trial, whether or not it is considered related to the device. This includes a change in a patient's condition or laboratory results which has or could have a deleterious effect on the patient's health or well-being.
- **Adverse Device Effect (ADE):** An adverse event related to study device(s).
- **Serious Adverse Event (SAE):** A SAE is an event:
 - Led to death
 - Led to a serious deterioration in the health of the patient that:
 - Resulted in life-threatening illness or injury
 - Resulted in permanent impairment of a body structure or a body function
 - Required in-patient hospitalization or prolongation of existing hospitalization
 - Resulted in medical or surgical intervention to arrest permanent impairment to body structure or a body function
 - Led to Chronic Disease
 - Led to fetal distress, fetal death or a congenital abnormality or birth defect
- **Unanticipated Adverse Device Effect (UADE):** Any serious adverse effect on health or safety or any life-threatening problem or death caused by, or associated with a device, if that effect, problem, or death was not identified in nature, severity or degree of incidence in the protocol or IFU or any other unanticipated serious problem associated with a device that relates to the rights, safety, or welfare of subjects.

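### Protocol 7.6.1 lets a relapse or expected progression of an undefined condition be recorded as an AE, in conflict with the outcome-based SAE definition in 7.6.1.2

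*Protocol*

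**What the plan says.** Protocol 7.6.1 (Adverse Events) contains this exemption: "An event does not need to be reported as a SAE if it represents a relapse or an expected change or progression of the condition". The next sentence reads "This type of event is considered an AE". The sentence just before the exemption deals with pre-existing conditions and procedures planned for them. The sentence after the reclassification requires every death to be reported.

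Protocol 7.6.1.2 (Definitions) defines an SAE by what the event led to. Besides death, its criteria include "Resulted in life-threatening illness or injury" and "Required in-patient hospitalization or prolongation of existing hospitalization". None of them is qualified by expectedness or disease progression.

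Three other rules in 7.6.1 bear on the consequence:

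- SAEs must be entered within 72 hours of site awareness; other reportable AEs need only be entered in a timely way.
- Seriousness is among the minimum data to record for each event.
- On late reporting: "After discharge and/or 7 day visit, all SAEs and neurological AEs are reportable through final follow-up visit". Section 6.9 applies the same limit to subjects still in hospital past Day 7.

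SAP 11.2 tabulates the number and percentage of subjects with AEs and SAEs.

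**The concern.** A site facing a non-fatal event that meets 7.6.1.2 but looks like progression has two rules with opposite answers. The choice decides whether the event goes through the SAE route (label, 72-hour entry, SAE report to the IRB/EC, SAE table) or is handled as an ordinary AE.

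The person choosing knows the treatment arm (Protocol 4.4). If the choice depends on whether the subject had surgery, the SAE rows of SAP 11.2 no longer compare like with like. Even if it does not, both SAE rates are understated. The protocol's own background cites between-arm SAE comparisons from earlier trials as safety evidence (46% against 60% in one, 126 against 142 events in another), and readers will use this trial's SAE table the same way.

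**Working it through.** The documents give no figure to reproduce, so the check is mainly a reading of the sections against each other.

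**1. Is there a conflict?** Take a non-fatal event that prolongs the hospital stay and is judged to be expected progression. Under 7.6.1.2 it is an SAE. Under 7.6.1 it need not be reported as one and is an AE. Neither section says which prevails.

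**2. Which condition is meant?** Two readings are open.

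- *Narrow: a pre-existing condition.* The preceding sentence supports this. The conflict remains, because a progressing comorbidity that leads to admission still meets 7.6.1.2.
- *Broad: the index ICH as well.* Nothing excludes it. Section 6.4 calls the stratification by Hemphill Score one on presenting condition, and section 3 (Risk Analysis) also uses the word for the disease under treatment. Section 3 lists "Brain Re-bleeding near Initial Hemorrhage Site" and "Cerebral Edema and Mass Effect" among expected events and explains: "Since these medical events are expected in the disease process or after MM, the events are thus expected to occur in any patients". Section 7.6.1 does not refer to that list, so the list makes the broad reading plausible without establishing it.

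**3. What happens to a downgraded event?**

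| | Neurological event | Non-neurological event |
|---|---|---|
| Up to discharge/Day 7 | Reportable as an AE; SAE label and 72-hour entry lost | Same |
| After discharge/Day 7 | Still reportable as an AE | Not reportable |
| Narrative and medical monitor review | Re-bleed, edema or ischemic stroke within 30 days that meets the 7.6.1 thresholds | Only surgical or anesthetic complications of MIS within 30 days |
| DSMB (Protocol 12.2) | Seen as an AE | Seen only if reported |
| SAE table (SAP 11.2) | Missing | Missing |

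Hydrocephalus has no narrative category of its own. Re-bleeds and edema below the thresholds or after 30 days have no narrative either.

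**4. Could the arms differ?** Section 7.6.1.3 reserves attribution to the index ICH for events with no time link to the device or treatment. A medically managed subject meets that easily; a recently operated subject does not. An investigator could therefore call a re-bleed progression more readily in the MM arm. This is an inference: attribution and the exemption are separate judgments. Section 7.6.1.3 also says that events more than 7 days after MIS are not expected to be procedure-related, so the contrast would be sharpest early.

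**5. Scale, on assumed inputs only.** Let *p* be the true rate of serious events that could be called progression, equal in both arms, and *d* the share downgraded in one arm only. The false difference is p − p(1 − d) = p × d. At N = 500 and 2:1 allocation the arms hold about 333 (MIS) and 167 (MM). The 95% half-width is 1.96 × √[a(1 − a)/333 + b(1 − b)/167], where *a* and *b* are the recorded rates in MIS and MM. The range depends on which arm is downgraded.

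| p | d | Recorded rate, affected arm | False difference (points) | 95% half-width (points) |
|---|---|---|---|---|
| 6.9% | 25% | 5.2% | 1.7 | 4.3–4.5 |
| 15% | 25% | 11.25% | 3.75 | 6.1–6.4 |
| 30% | 25% | 22.5% | 7.5 | 8.0–8.3 |
| 30% | 50% | 15.0% | 15.0 | 7.3–7.9 |

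The 6.9% is the re-bleeding rate of the predecessor device (2/29, Protocol section 3), used only as a low anchor. The other values of *p*, and every *d*, are assumptions. The sign depends on which arm is downgraded. Equal downgrading of 25% at p = 30% gives no difference but lowers both recorded rates from 30% to 22.5%.

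**The case against.** The strongest reply is that the sentence concerns pre-existing conditions, as its position suggests, and that the rest of the safety system covers the index ICH. Seriousness is a required field. Neurological AEs stay reportable to the end of follow-up. Threshold events within 30 days get narratives. The DSMB receives all reported AEs and SAEs. Under SAP 11.2, data adjudicated by the Clinical Events Committee (CEC) replace investigator data in every adverse event analysis. The primary safety endpoint is 30-day mortality, and SAP 11.3 keeps other safety comparisons unadjusted and out of labeling claims.

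Much of this stands, and it limits the point. It does not remove it:

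- The narrow reading is possible but not stated, and it still conflicts with 7.6.1.2.
- A seriousness field does not help if 7.6.1 tells the site that the event is not to be handled as an SAE.
- The CEC's stated task is causality and attribution (Protocol section 3, SAP 16.1). Protocol 11.2.2 also has it set rules for classifying clinical events. Neither says that it decides seriousness.

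A reader might infer three stronger things that the documents do not support. First, that every listed expected event, including pneumonia, sepsis and pulmonary embolus, is exempt: 7.6.1 exempts relapse or progression, not all expected events, and does not invoke the list. Second, that downgraded re-bleeds and edema disappear from DSMB view: they remain reportable and reach the DSMB as AEs. Third, that the SAE comparison is biased in a known direction: the sentence applies to both arms, and nothing fixes the sign or size.

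**Conclusion.** The conflict between 7.6.1 and 7.6.1.2 is real on either reading. If the condition includes the index ICH, serious non-fatal re-bleeds, edema or hydrocephalus can lose the SAE label, the 72-hour entry and their place in the SAE table, on the judgment of someone who knows the arm. The only outright loss is a non-neurological event downgraded after discharge or Day 7, and that is most plausible for progression of a comorbidity.

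The size cannot be calculated from the documents. The assumed cases give false differences of 1.7 to 15 points if only one arm is affected, and none if both are affected equally. Differential classification is a possibility, not a finding. Deaths, 30-day mortality and the primary efficacy endpoint are untouched. The sponsor should correct the wording, but it does not threaten the trial's main conclusions.

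**What to change.** Reconcile 7.6.1 with 7.6.1.2:

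1. Delete the exemption and the reclassifying sentence after it. Alternatively, limit them explicitly to pre-existing conditions other than the index ICH, and only where the event does not meet 7.6.1.2.
2. State that any event meeting 7.6.1.2 is reported as an SAE in both arms, whether or not it was expected.
3. Record expectedness in a separate field that has no effect on the SAE label.
4. State whether the CEC adjudicates seriousness, since SAP 11.2 gives its data precedence.

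The cost is a protocol amendment with the approvals in section 12.4, site retraining and somewhat more SAE forms. Treatment, endpoints and sample size do not change.

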1.3 Rationale for Study

ICH is thought to induce neurological injury in a biphasic manner.²⁹ The primary neurological injury is caused by the direct mechanical destruction of neurons by the original bleed.² This form of injury is not treatable *per se*, with the exception

perhaps of medical interventions designed to reduce or eliminate hematoma early expansion from re-bleeding. As discussed above, several medical interventions have been demonstrated to successfully limit hematoma growth, but none have been associated with a compelling clinical benefit.

Secondary injury to the brain surrounding the hematoma has been theorized to be the sequelae of locally increased pressure resulting in reduced regional perfusion as well as a direct cytotoxic effect of blood breakdown products on adjacent brain tissue (hemotoxicity).²⁹ It is believed that this secondary injury is manifested as peri-hematomal edema (PHE) on imaging studies.³⁰⁻³³

In patients with ICH undergoing serial CT studies over the course of several weeks, Zazulia et al. observed the progression of mass effect at two distinct time periods. Early exacerbation of mass effect (within 48 hours) was related to acute hematoma expansion.³³ Later progression was the result of peri-hematomal cerebral edema, which occurred between 9 and 21 days after the original bleed.³³ This delayed progression of edema and mass effect from days to weeks after ICH provides strong supportive clinical evidence of a secondary injury. Other investigators have also observed that mass effect and cerebral edema persists longer after ICH than ischemic stroke, with mass effect lasting for up to one month in some cases.³⁴⁻³⁷

Studies of regional perfusion in humans have largely failed to demonstrate significant regions of ischemia in the brain surrounding ICH.^{38,39} On the contrary, a wealth of pre-clinical evidence has shown that thrombin, hemoglobin, iron and other hemoglobin breakdown products have a significant potential for direct toxic effects upon brain tissue.⁴⁰⁻⁴²

Theoretically, the early evacuation of blood products could alleviate local mass effect and improve regional perfusion, and, in addition, reduce the volume of blood products and substrate contributing to hemotoxicity, thus reducing or eliminating these potential mechanisms of secondary injury. At the same time, the procedure would be best done in the least invasive manner possible as to avoid inducing additional injury to the brain.

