- Symptomatic Re-Hemorrhage or New Hemorrhagic Event: Any new intracranial hemorrhage or increase in size of pre-existing hemorrhage (IPH, IVH or extra-axial bleed) within 30 days associated with an NIHSS increase of ≥ 4 or a GCS decrease > 2 persisting for at least 24 hours, requiring emergency surgical decompression or resulting in death.
- Symptomatic Evolution of Perihematomal Edema: Edema with increased mass effect or uncontrolled ICPs within 30 days requiring emergency surgical decompression NOT related to new or increased hemorrhage (i.e. edema related) associated with an NIHSS increase of ≥ 4 or a GCS decrease > 2 persisting for at least 24 hours, requiring emergency surgical decompression or resulting in death.
- Symptomatic Ischemic Stroke: A new ischemic stroke (ipsilateral, contralateral; contiguous with bleed/operative site or remote; cortical, subcortical or perforator distribution) within 30 days associated with an NIHSS increase of ≥ 4 or a GCS decrease > 2 persisting for at least 24 hours, requiring emergency surgical decompression or resulting in death.
- Surgical complications related to MIS: Surgical site infection, brain abscess or confirmed meningitis, or documented complication(s) deemed specifically related to the procedural anesthetic (medication, access or intubation related) within 30 days.

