12.2 Stopping the Trial Based on Interim Safety Data

The DSMB will receive periodic safety reports of all reported AEs and SAEs. In addition, the following specific endpoints will be assessed by the medical monitor and presented:

- Death (all cause) within 30 days of enrollment
- Death within 7 days of enrollment: Immediate periprocedural death
- Symptomatic Re-Hemorrhage or New Hemorrhagic Event: Any new intracranial hemorrhage or increase in size of pre-existing hemorrhage (IPH, IVH or extra-axial bleed) within 30 days associated with an increase of 4 or more points on the NIHSS or GCS decrease > 2 persisting for at least 24 hours, requiring emergency surgical decompression or resulting in death
- Symptomatic Evolution of Perihematomal Edema: Edema with increased mass effect or uncontrolled ICPs within 30 days requiring emergency surgical decompression NOT related to new or increased hemorrhage (i.e., edema related) associated with an increase of 4 or more points on the NIHSS or GCS decrease > 2 persisting for at least 24 hours, requiring emergency surgical decompression or resulting in death
- Symptomatic Ischemic Stroke: A new ischemic stroke (ipsilateral, contralateral; contiguous with bleed/operative site or remote; cortical, subcortical or perforator distribution) within 30 days associated with an increase of 4 or more points on the NIHSS or GCS decrease > 2 persisting for at least 24 hours, requiring emergency surgical decompression or resulting in death
- Surgical complications related to MIS: Surgical site infection, brain abscess or confirmed meningitis, or documented complication(s) deemed specifically related to the procedural anesthetic (medication, access or intubation related) within 30 days

Additional details regarding the DSMB structure and stopping rules will be included in the DSMB charter.

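### On its natural reading, the symptomatic perihematomal edema event (Protocol 7.6.1 and 12.2) admits only surgically decompressed cases, unlike the two parallel events

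*Protocol*

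**What the plan says.** Protocol 7.6.1 lists six specific events for which a detailed form and narrative are obtained. Section 7.6.1.1 has a medical monitor review them as they are reported. Section 12.2 repeats the list as endpoints to be presented to the DSMB.

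The edema event begins: "Edema with increased mass effect or uncontrolled ICPs within 30 days requiring emergency surgical decompression NOT related to new or increased hemorrhage". It continues: "i.e. edema related) associated with an NIHSS increase of ≥ 4 or a GCS decrease > 2 persisting for at least 24 hours, requiring emergency", and the sentence ends by naming surgical decompression or death. Section 12.2 words the NIHSS change slightly differently but has the same structure, with decompression named twice.

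The two parallel events use the same closing conditions but do not mention decompression in their opening:
- Re-hemorrhage: "Any new intracranial hemorrhage or increase in size of pre-existing hemorrhage (IPH, IVH or extra-axial bleed) within 30 days associated with an NIHSS increase"
- Ischemic stroke: "cortical, subcortical or perforator distribution) within 30 days associated with an NIHSS increase of ≥ 4 or a GCS decrease > 2"

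The same list contains "Death (all cause) within 30 days of enrollment". On general reporting, 7.6.1 says "After discharge and/or 7 day visit, all SAEs and neurological AEs are reportable through final follow-up visit", and 12.2 says "The DSMB will receive periodic safety reports of all reported AEs and SAEs".

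**The concern.** Decompression is both an entry condition and one of the closing alternatives. If it is already required for entry, the later mention of decompression and the mention of death cannot bring in any further case. A subject who dies of edema without surgery, or who deteriorates and is managed without it, falls outside the category. The same course after a re-bleed or a new infarct could fall inside its category.

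The category bears on the trial's rationale. Section 1.3 treats perihematomal edema as the visible sign of secondary injury, and says of mass effect: "Later progression was the result of peri-hematomal cerebral edema, which occurred between 9 and 21 days after the original bleed". Section 4 makes prevention of secondary injury the primary aim of the procedure. Section 4.4 states that investigators and site staff know the assignment. A count that depends on surgery is therefore partly a count of unblinded decisions to operate, and those may differ between arms for reasons other than edema.

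**Working it through.** The plan gives no rate, sample size or error level for this event, so there is no figure to reproduce. The check is one of logic.

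**Inputs** (7.6.1, repeated in 12.2). Take five yes/no facts, all within 30 days and not hemorrhage related: M = increased mass effect, P = uncontrolled ICP, S = emergency decompression, W = NIHSS/GCS worsening lasting at least 24 hours, D = death. There are 2^5 = 32 combinations. These are logical cases, not patient frequencies.

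**Current wording, four readings**

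| Reading | Rule | Qualify | Of these, without surgery |
|---|---|---|---|
| 1. Decompression governs the whole opening; closing conditions are alternatives | (M or P) and S and (W or S or D) | 3 × 4 = 12 | 0 |
| 2. Same opening; worsening is required together with surgery or death | (M or P) and S and W and (S or D) | 3 × 2 = 6 | 0 |
| 3. Decompression attached to uncontrolled ICP only; alternatives | (M or (P and S)) and (W or S or D) | 12 + 6 = 18 | 2 × 3 = 6 |
| 4. As 3, but joint conditions | (M or (P and S)) and W and (S or D) | 6 + 2 = 8 | 2 × 1 = 2 |

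Reading 1 reduces exactly to (M or P) and S, so W and D add nothing. In reading 2, D again adds nothing and W only narrows the event. Readings 1 and 2 are the natural ones, because the decompression phrase follows the 30-day window, which applies to mass effect and ICP alike. Readings 3 and 4 are strained but possible.

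**Opening written like the parallel events (no S in the opening)**

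| Closing conditions | Rule | Qualify | Of these, without surgery |
|---|---|---|---|
| Alternatives | (M or P) and (W or S or D) | 12 + 9 = 21 | 3 × 3 = 9 |
| Joint | (M or P) and W and (S or D) | 6 + 3 = 9 | 3 × 1 = 3 |

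**What the opening clause removes.** With alternatives, 21 − 12 = 9 combinations go: 6 include death, 6 include worsening and 3 include both (6 + 6 − 3 = 9). With joint conditions, 9 − 6 = 3 go, all fatal with worsening. So, on the natural reading, fatal edema with deterioration and no surgery is excluded however the closing conditions are read. Non-fatal deterioration without surgery is treated differently from the parallel events only if the closing conditions are alternatives.

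**Where an excluded case still appears**
- Death within 30 days: the all-cause death item on the same list, with the same form, narrative, monitor review and DSMB presentation. Section 7.6.1 requires the primary condition behind a death to be reported as an SAE, and 11.2.2 has the CEC rule on all deaths.
- Non-fatal: reportable as an AE up to discharge or Day 7, and as a neurological AE or SAE afterwards. However, 7.6.1 lets expected progression of the condition be reported as an AE instead of an SAE, and Section 3 lists cerebral edema and mass effect among expected events.
- SAP 11.2 tabulates AEs by body system and preferred term, for categories reported by at least 3% of subjects (0.03 × 500 = 15 subjects at full enrollment). That does not rebuild an edema count using the protocol's NIHSS/GCS thresholds.

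**The case against.** The strongest reply is that little depends on this count. It is not a primary or secondary endpoint (4.2), and the SAP sets no comparison for it. SAP 11.3 makes all safety comparisons other than the primary one secondary, unadjusted and not for labeling. The stopping rules mentioned in 7.6.1.1 concern the primary safety endpoint, which is 30-day mortality. The CEC sets its own classification criteria (11.2.2) under a charter not among the documents, so the literal wording may not be what is applied. All of this stands. It limits the consequence but does not make the definition coherent, and the DSMB still receives the category by name.

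A reader might go further and infer that edema deaths go uncounted. The documents do not support that: they are counted as deaths, with cause reported and adjudicated. What is lost is their appearance as edema events.

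A reader might also infer that the count is bound to favor MIS. No edema rate or decompression fraction is given for either arm. Assume, for illustration, a true rate of 8% in both arms. If 30% of MIS and 50% of MM cases were decompressed, recorded rates would be 0.08 × 0.30 = 2.4% and 0.08 × 0.50 = 4.0%. Reversing the fractions gives 4.0% and 2.4%, and equal fractions give no difference. The direction is an assumption, not a finding.

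**Conclusion.** The definition is faulty as written. On the natural reading, no edema case without emergency decompression can enter the category, and the death condition is redundant. On the strained reading some can, so sites and adjudicators could classify the same case differently. The parallel definitions make a drafting slip likely, though an intended surgery-only event cannot be excluded.

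The consequence is confined to the edema category count by arm, with its narratives, as seen by the medical monitor and the DSMB. Its size and direction cannot be derived from the documents. The conclusion assumes that the protocol text governs classification; CEC criteria that already depart from it would lessen the effect. Primary efficacy and the 30-day mortality endpoint are not touched.

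**What to change.** In Protocol 7.6.1 and 12.2, reconcile the edema event with the re-hemorrhage and ischemic stroke events. Delete the first of the two decompression clauses, the one between the 30-day window and the exclusion of hemorrhage-related cases, so that the existing closing conditions work as they do in the parallel events. Carry the change into the CEC criteria. If a surgery-only event was intended, say so, remove the redundant closing conditions and retitle the event.

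The sponsor should also state whether the closing conditions are alternatives or joint requirements, and apply the answer to all three definitions. That choice, like the clinical thresholds, is the sponsor's.

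The cost is wording in two protocol sections and the CEC criteria, somewhat more events to write up, and a higher recorded edema rate than under the present text. Decompression would remain one qualifying condition, so the influence of unblinded surgical decisions is reduced, not removed. Only what is counted changes, not how subjects are treated.
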